We estimated a pre-defined 8-point non-inferiority margin, based on a significant effect of the COGNI-TRAcK in inducing an about 8-point mean increase at SDMT score (with respect to a sham intervention). Accordingly, 35 subjects per arm are required to ensure, with an approximately 85%-power level, that the lower limit of a one-side 95% confidence interval will be above the pre-defined non-inferiority margin. Therefore, considering also a drop-out rate of 25%, a total of 132 subjects should be enrolled.

Statistical methods

All analysis will be based on the intention-to-treat principle using the fully analysis dataset including all randomized patients. Missing data will be handled by multiple imputation method. Continuous data will be analyzed by parametric and non-parametric RM-ANOVAs with effect size estimation. The time-to-event data will be analyzed by Kaplan-Meier curves and Log-Rank test with a factor for treatment group.

An interim analysis will be conducted when at least 50% of the estimated sample size will complete the 8-week intervention period.

Study objectives

Primary objective	Primary endpoint
To demonstrate not inferior efficacy of exergames over COGNI-TRAcK and superior efficacy of both interventions over sham in improving sustained attention and information processing speed	Change at the SDMT from baseline to Week 8
Secondary objectives	Secondary endpoints
To demonstrate not inferior efficacy of exergames over COGNI-TRAcK and superior efficacy of both interventions over sham in improving cognitive functions	Change at the BICAMS and SCWT from baseline to Week 8
Additional objectives	Additional endpoints
To demonstrate not inferior efficacy of exergames over COGNI-TRAcK and superior efficacy of both interventions over sham in reducing the impact of MS on: - cognitive-motor interference - activities of daily living - fatigue - work productivity	Change of dual-task cost of walking and balance as estimated by the 2MWT and static posturography in dual-task vs. single-task condition from baseline to Week 8 Change at the MSIS-29 from baseline to Week 8 Change at the MFIS from baseline to Week 8 Change at the WPAI:MS from baseline to Week 8
Exploratory objectives	Exploratory endpoints
To demonstrate not inferior efficacy of exergames over COGNI-TRAcK and superior efficacy of both interventions over sham on: - physical activity - adherence	Physical activity measured by wearable actigraph Percentage of training completed at home

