
Rationale for study design and duration

This is a multi-centre, 16-week (8-week intervention followed by 8-week follow-up), randomized, single-blind, parallel-arm study comparing three different types of home-based training:

- (1) active video games of balance delivered by the Wii balance board, from here onwards called **‘exergames’** (intervention of interest);
- (2) Cognitive Training Kit (COGNI-TRAcK) with increasing difficulty levels, from here onwards called **‘adaptive COGNI-TRAcK’** (comparator intervention);
- (3) COGNI-TRAcK at constant difficulty level, from here onwards called **‘sham COGNI-TRAcK’** (placebo-analogue intervention) [24].

This study design will allow us to test the hypotheses that (i) exergames and adaptive COGNI-TRAcK are more effective than sham adaptive COGNI-TRAcK; (ii) exergames are not inferior to adaptive COGNI-TRAcK.

The choice of an 8-week study duration was based on previously published papers on cognitive training delivered by COGNI-TRAcK. In this study, 8 weeks of adaptive COGNI-TRAcK training were sufficient to determine a significant improvement in the SDMT score when compared with sham COGNI-TRAcK, yielding to a post-training between-arm difference of 8 points ($p < 0.001$) [24].

The 8-week post-training follow-up period will allow us to investigate the retention of training effect, which is an underinvestigated topic in MS rehabilitation setting. Literature data provide conflicting results (no retention for exergames, 6-month retention for cognitive rehabilitation) [9],[24].

Rationale for interventions

Exergames (the portmanteaux for “exercise” and “video games”) represent a form of whole-body physical exercise performed through active video games. Playing exergames involves not only the hand-eye coordination, but also whole body physical exertion, with the aim of improving fitness and promoting an active lifestyle [8]. Unlike the fully immersive VR (that simulates a lifelike multisensorial experience in a 3-dimensional artificial environment), the non-immersive VR involves the use of smaller-scale, 2-dimensional environment (e.g. home TV, computer display, etc) and interface devices, such as balance board, motion controllers or cameras equipped with depth sensors that can also provide haptic or kinesthetic communication reproducing tactile sensations by applying forces, vibrations or motions [7].

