A recent meta-analysis exploring the role of exergames in improving cognitive functions in persons suffering from neurological disabilities (including MS), showed that exergames significantly improved executive functions and visuo-spatial perception when compared to alternative or no intervention [22]. Therefore, exergames can represent a highly-flexible tool to rehabilitate both cognitive and motor functions by means of an unique training.

COGNI-TRAcK is a low-cost, user-friendly application software (app) for portable devices (mobile phone and tablet) that delivers a self-administered, intensive and monitored cognitive training based on working memory exercises. The main feature of COGNI-TRAcK is the implementation of automatic adaptive working load algorithms and procedures for intensiveness regulation. Moreover, it can be easily used at home enhancing the possibility to schedule an intensive training and ensuring adherence to treatment. Preliminary data showed that COGNI-TRAcK is highly usable, motivating and well-accepted by patients with MS [25]. Adaptive COGNI-TRAcK (i.e. automatic adjustment of tasks difficulty) has been found superior over sham COGNI-TRAcK (i.e. constant difficulty level) in verbal memory acquisition and delayed recall, verbal fluency, sustained attention, concentration and information processing speed [24]. Therefore, sham COGNI-TRAcK can be used as placebo-analogue arm in order to avoid ethical concerns and a possible unmotivating effect of wait-list group.

Rationale for study endpoints

The SDMT (primary endpoint) represents a simple screening test for cognitive impairment [26],[27]. An improvement of 4 points or 10% in magnitude is considered clinically relevant [28].

The Brief International Cognitive Assessment for MS (BICAMS) (secondary endpoint) has been recently developed as brief, practical and universal assessment tool for cognitive impairment in MS; it includes the SDMT, the California Verbal Learning Test-2 (CVLT2) and the Brief Visuospatial Memory Test–Revised (BVMT-R) [29]. To test some aspects of executive functions not explored by the BICAMS, the Stroop Color-Word Test (SCWT) is also included in the assessment [30].

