No pharmacological treatment is strictly forbidden; however, patients are encouraged to not start pharmacological treatments that can potentially impact on cognition, namely antidepressants, dalfampridine, nabiximols, modafinil, amantadine, dopamine-agonists.

Steroid administration due to MS relapse or any symptomatic drug initiation due to any MS-related symptom should be considered as an AE.

Patients are encouraged to not start any other type of physiotherapy or rehabilitation during the study period, but they are encouraged to continue his/her physiotherapy or rehabilitation program if started at least 3 months before the study enrolment.

STATISTICAL PLAN

Sample size estimation

Overall, we will randomize **126 patients** (considering even a 20% drop-out rate), based on two previously published studies that have found:

- (i) a significant effect of an home-based cognitive training using the [name]® Brain Training that promoted an about 8-point mean increase at SDMT score (with respect to wait-list group) [53];
- (ii) a significant effect of adaptive COGNI-TRAcK that promoted an about 8-point mean increase at SDMT score (with respect to a sham intervention) [24];
- (iii) a 50%-difference in proportions of responders (10/14 versus 3/14 in adaptive COGNI-TRAcK group and sham COGNI-TRAcK group, respectively) [24], according to a responder definition of SDMT change approximating 4 points or 10% in magnitude [28].

For the non-inferiority comparison, the null hypothesis is that the intervention with exergames is inferior to adaptive COGNI-TRAcK, while the alternative hypothesis is that the intervention with exergames is non-inferior to adaptive COGNI-TRAcK by a pre-defined amount of SMDT score.

If there is truly no difference between exergames and adaptive COGNI-TRAcK, then 35 patients per arm are required to ensure, with a statistical power of approximately 85%, that the lower limit of a one-sided 95% confidence interval (or equivalently a 90% two-sided confidence interval) will be above the predefined non-inferiority margin of 8-point change in SDMT.

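### The 8-point non-inferiority margin equals the whole cited adaptive-versus-sham effect, so meeting it does not show that exergames keep any of the comparator's benefit, and the claim is not made conditional on beating sham

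*Protocol*

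**What the plan says.** Under Statistical plan, Sample size estimation, the protocol assumes no true difference between exergames and adaptive COGNI-TRAcK. It requires 35 patients per arm for about 85% power that the lower limit of a one-sided 95% interval "will be above the predefined non-inferiority margin of 8-point change in SDMT". No SD is given.

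The synopsis states where the margin comes from: "We estimated a pre-defined 8-point non-inferiority margin, based on a significant effect of the COGNI-TRAcK in inducing an about 8-point mean increase" in SDMT score relative to sham. The rationale for study design and duration reports the same earlier trial as "yielding to a post-training between-arm difference of 8 points", with p < 0.001.

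The rationale for study endpoints sets the scale of what matters: "An improvement of 4 points or 10% in magnitude is considered clinically relevant".

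The primary objective joins non-inferiority to adaptive COGNI-TRAcK with superiority of both interventions over sham, and the section on the significance level plans both sham comparisons at two-sided 0.025. The only superiority comparison that is sized is adaptive versus sham, on the proportion of responders. No sentence makes the non-inferiority claim depend on either sham comparison.

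**The concern.** A non-inferiority margin is the largest loss against the comparator that one agrees to tolerate. If it equals the comparator's whole advantage over sham, the tolerated loss is everything the comparator is believed to achieve. Excluding that loss shows at most that some effect over sham remains. It does not show that a worthwhile part of the adaptive training effect is kept, which is what a reader takes from a claim of being not inferior.

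The protocol gives no retained fraction, no confidence limit for the comparator effect and no clinical argument for 8 points. Its own relevance threshold is half that size. This is not detail left for an analysis plan: the protocol fixes the margin and states its basis, and the main conclusion for the intervention of interest depends on it.

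**Working it through.** **Inputs from the protocol.** Margin 8 points; cited adaptive-versus-sham effect about 8 points; clinically relevant change 4 points; 35 per arm; one-sided 5%; power about 85%; assumed true difference 0; sham comparisons at two-sided 0.025.

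**Share of the effect preserved.** Margin / effect = 8/8 = 100%, so 1 − 100% = 0% is preserved. Against the relevance threshold, 8/4 = 2.

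**The plan's own figure.** Without an SD, 35 per arm cannot be reproduced, only inverted (normal approximation):

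SD = 8 × √(35/2) / (1.645 + 1.036) = 12.48.

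A t-based calculation gives 12.36. An SD of 12.4 returns 35 per arm with 85.4% power. The stated design therefore implies an SD of about 12.5.

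**Decision rule in observed terms.** SE = 12.48 × √(2/35) = 2.98. Non-inferiority is declared when the observed difference (exergames minus adaptive) exceeds −8 + 1.645 × 2.98 = −3.1 points.

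**Chance of declaring non-inferiority** for a true loss d: Φ((8 − d)/2.98 − 1.645).

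| True loss against adaptive | Chance of declaring non-inferiority |
|---|---|
| 0 | 85% |
| 4 (half the cited effect) | 38% |
| 6 | 16% |
| 7 | 9.5% |
| 8 (equal to sham if the adaptive effect is 8) | 5% |

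If the true adaptive effect is smaller than 8, an exergames arm equal to sham loses only that smaller amount. By the same formula it passes 16% of the time if the effect is 6, 26% if it is 5 and 38% if it is 4. These smaller effects are assumed values.

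**Adding the sham condition.** I simulated three independent arm means (35 per arm, SD 12.48, normal tests) and required non-inferiority plus superiority of each active arm over sham at two-sided 0.025:

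- Exergames equal to sham, true adaptive effect 8: the false claim falls from 5% to about 0.4%.
- Exergames equal to sham, true adaptive effect 4: it falls from 38% to about 0.7%.
- Both active arms truly 8 points better than sham: all three conditions are met about 47% of the time with the 8-point margin and about 18% with a 4-point margin.

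**A 4-point margin at 35 per arm.** Power for non-inferiority alone is Φ(4/SE − 1.645): 38% at SD 12.5, 58% at SD 9 and 88% at SD 5.9. SD 9 is an assumed middle value. SD 5.9 is what the cited responder rates (10/14 and 3/14) would imply for an 8-point shift, assuming normal changes and equal SDs: 8/1.358 = 5.89. At SD 12.48, 85% power would need 35 × (8/4)² = 140 per arm.

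**The case against.** The strongest reply is that this is a three-arm trial with a concurrent sham. The risk of preserving nothing is gravest in two-arm trials, where the comparator's effect must be taken from history. Here the primary objective already asks for superiority of both interventions over sham, and both comparisons are planned. If the whole objective had to be met, an arm equal to sham would almost never succeed. This stands in part: a reader might infer that the non-inferiority result would be uninterpretable, and the documents do not support that. The safeguard is nevertheless not written as a condition, exergames versus sham is not sized, and beating sham would still not show how much of the comparator's effect is retained.

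Three other stronger readings are also unsupported.

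- **Exergames could readily pass while no better than sham.** If the adaptive effect is truly 8, that error is held at 5% by construction. It grows only if the effect is smaller. What holds in either case is that an arm little better than sham can pass.
- **The comparator effect has a lower 95% limit of about 3.6 points.** That figure treats p as exactly 0.001 and assumes a two-sample t-test with 14 per arm. The protocol says p < 0.001 and does not name the test, so 3.6 is only a floor.
- **Non-inferiority would be declared 88% of the time at a true loss of 4, and 41% at a loss of 6.** These figures need an SD of 5.9. At that SD, 35 per arm would give power above 99.9% for the 8-point margin, which conflicts with the stated 85%.

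Finally, the protocol uses 4 points as a relevance and responder threshold, not as a between-arm margin. Nothing in it makes 4 the only defensible choice.

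**Conclusion.** The point holds. The margin is the full point estimate of the comparator's effect and twice the protocol's relevance threshold, and no text makes the claim conditional on beating sham. Followed as written, the rule declares non-inferiority 38% of the time when half the cited effect is lost and 16% when three quarters is lost.

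These figures rest on 35 evaluable patients per arm, normal approximations, an adaptive effect of 8 points and an SD of about 12.5 inferred from the stated power. The finding that 0% of the effect is preserved rests on none of these except the cited 8 points. The threshold is wrong for the claim attached to it. The trial as a whole is not uninterpretable, because the sham arm can repair much of the problem once it is tied to the claim.

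**What to change.** 1. State that non-inferiority may be claimed only if adaptive COGNI-TRAcK and exergames each beat sham on Week-8 SDMT change. Both comparisons are already planned, so this needs wording and no new procedures.
2. Replace the 8-point margin with one that retains a justified share of the effect. Four points would retain half of the point estimate and match the protocol's relevance threshold; another value needs its own argument. Write the criterion as a lower limit above minus the margin.
3. State the SD and its source, and restate the power at 35 per arm, both for non-inferiority alone and jointly with the two sham comparisons.

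**Cost.** The text changes are cheap; the loss of power is not, and it should be disclosed. At SD 12.5, requiring all three results leaves joint power of about 47% even with the 8-point margin. With a 4-point margin, non-inferiority power is about 38% (58% at SD 9, 88% at SD 5.9) and joint power about 18% at SD 12.5. At that SD, exergames would have to be observed ahead of adaptive training to pass: −4 + 1.645 × 2.98 = +0.9 points. Restoring 85% power for non-inferiority alone would take about 140 per arm.

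If the sponsor keeps 8 points, the protocol should limit the conclusion to having excluded a loss of the full cited effect, and should not describe exergames as not inferior to adaptive COGNI-TRAcK without that qualification.

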Patients with MS, regardless of disease course, who fulfil all inclusion criteria and none of the exclusion criteria, will be randomized in a 1:1:1 ratio to exergames or adaptive COGNI-TRAcK or sham COGNI-TRAcK. This study includes two periods (training period and follow-up period) and three visits (see the **FIGURE** below):

- on Week 0, at study enrolment/randomization (baseline visit);
- on Week 8 (+/- 5 days), i.e. after the end of the 8-week training period (Week 8 visit);
- on Week 16 (+/-5 days), i.e. at study termination after the 8-week post-training follow-up period (Week 16 visit).

Eligibility criteria

For inclusion:

- (i) age between 18 and 55 years (inclusive);
- (ii) cognitive impairment, defined as failure in the SDMT, defined as a corrected score less than 38, i.e. below the 5th percentile of normative value [31];
- (iii) Expanded Disability Status Scale (EDSS) score between 2.0 and 5.5 [32];
- (iv) ability to stand upright for at least 180 seconds without any support;
- (v) ability to understand and comply with study requirements;
- (vi) ability to provide a valid informed consent before any study procedure.

For exclusion:

- (i) relapse in the previous 6 months;
- (ii) initiation of disease-modifying or symptomatic treatments or physiotherapy programme in the 3 months prior to study entry;
- (iii) any medication/physiotherapy changes occurring over the previous 3 months;
- (iv) significant visual impairment, defined as a Visual System scoring more than 2 at the Kurtzke Functional Systems Score [32];
- (v) clinically relevant depression, defined as Beck Depression Inventory-II (BDI-II) score equal or more than 14 [33];
- (vi) overt dementia, defined as an adjusted Mini Mental State Examination (MMSE) score equal or less than 24 [34];
- (vii) history of epilepsy or seizures;
- (viii) any medical condition, including musculoskeletal disorders that can interfere with the study conduction.

Randomization procedure

Randomization codes will be computer-generated in blocks of six to ensure an approximate 1:1:1 balance between the three arms. Randomization codes will be assigned at baseline visit sequentially within each center as patients become eligible for randomization by an independent organization not involved in study conduction. Once a block is exhausted, the next available block will be allocated to a center upon the next randomization.

Blinding

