For the superiority comparison, the null hypothesis is that the intervention with adaptive COGNI-TRAcK is not superior to sham COGNI-TRAcK, while the alternative hypothesis is that the intervention with adaptive COGNI-TRAcK is superior to sham COGNI-TRAcK in increasing the proportion of responders as afore defined. Enrolling 35 patient per arm will ensure a more than 95% power in detecting a statistical significance between-group difference of 50% at two-sided alpha level of 5%.

Statistical analysis

All analysis will be based on the intention-to-treat principle using the fully analysis dataset including all randomized patients. Missing data will be handled by multiple imputation method, with the assumption that some data will be missed completely at random.

Efficacy analyses: efficacy data will be analyzed by parametric and/or non-parametric Repeated Measures Analyses of the Variance (RM-ANOVAs) with effect size estimation. In each analysis, we will consider as dependent variable all measures or score derived from study assessments; the three study visits (Baseline, Week 8 and Week 16) as within-subject factors; and intervention arms (exergames, adaptive COGNI-TRAcK and sham COGNI-TRAcK) as between-subject factors. Effect sizes will be estimated as Cohen's F-squared, rated as small, medium, and large for values of 0.02, 0.15, and 0.35, respectively [54].

Safety data regarding time to first accidental falls will be analyzed as time-to-event data by Kaplan-Meier curves and Log-Rank test with a factor for intervention arms.

Safety analyses: data regarding the occurrence of adverse events during the intervention period and the follow-up period will be analyzed by the Chi-squared test comparing the independent distribution of events according to intervention arms.

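### The superiority power of more than 95% is for an adaptive-versus-sham responder comparison, not for the planned SDMT-change tests of both trainings against sham

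*Protocol*

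**What the plan says.** The study objectives in the Protocol Synopsis give the primary objective as non-inferiority of exergames to COGNI-TRAcK together with "superior efficacy of both interventions over sham in improving sustained attention and information processing speed". The primary endpoint is "Change at the SDMT from baseline to Week 8".

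The Sample size estimation section of the Statistical Plan powers non-inferiority on SDMT points. It uses a margin of 8 points, 35 patients per arm, about 85% power and a one-sided 95% confidence limit, assuming no true difference between exergames and adaptive COGNI-TRAcK. For superiority it changes outcome: the hypothesis is that "the intervention with adaptive COGNI-TRAcK is superior to sham COGNI-TRAcK in increasing the proportion of responders as afore defined". The input is "a 50%-difference in proportions of responders (10/14 versus 3/14 in adaptive COGNI-TRAcK group and sham COGNI-TRAcK group, respectively"), and the conclusion is "Enrolling 35 patient per arm will ensure a more than 95% power in detecting a statistical significance between-group difference of 50" percentage points, at a two-sided alpha of 5%.

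The Statistical analysis section analyses efficacy by parametric and/or non-parametric repeated-measures ANOVA, with measures or scores as the dependent variable, three visits and three arms. The significance-level section applies Bonferroni for the two comparisons with sham, giving a two-sided threshold of 0.025. Achieving a clinically relevant change appears as an outcome only in the logistic regressions on the CRIQ, HLAQ and TCI scores. Intervention arm is not among the covariates listed for those models.

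**The concern.** The powered superiority test and the planned superiority tests differ in three ways: the outcome (responder proportion against SDMT change as a score), the comparisons covered (adaptive versus sham only, against both trainings versus sham) and the significance level (5% against 0.025).

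A reader would naturally take more than 95% as the chance that the trial confirms its primary superiority claim. The protocol contains no calculation that supports this. Exergames is the intervention of interest, yet its comparison with sham has no power statement in the synopsis or the Statistical Plan. That comparison carries weight because the non-inferiority margin of 8 points equals the whole adaptive-versus-sham effect cited. Meeting non-inferiority would not by itself show that exergames beat sham.

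**Working it through.** **1. The plan's own figure.** Inputs from Sample size estimation: p1 = 10/14 = 0.714, p2 = 3/14 = 0.214, n = 35 per arm, two-sided alpha 0.05. The pooled proportion is 0.464.

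- SE under the null = sqrt(2 × 0.464 × 0.536 / 35) = 0.1192
- SE under the alternative = sqrt((0.714 × 0.286 + 0.214 × 0.786) / 35) = 0.1032
- Power at 5% = Phi((0.500 − 1.960 × 0.1192) / 0.1032) = Phi(2.58) = 99.5%
- Power at 0.025 (critical value 2.241) = Phi(2.26) = 98.8%

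Exact enumeration with Fisher's test gives 98.5% at 5% and 97.1% at 0.025. The claim of more than 95% is correct for the test it describes.

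**2. Powered test beside planned test.**

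| | Power statement | Planned primary superiority |
|---|---|---|
| Outcome | responder proportion | SDMT change, as a score |
| Comparisons | adaptive vs sham | adaptive vs sham and exergames vs sham |
| Two-sided alpha | 0.05 | 0.025 |

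**3. Power on the planned scale.** The protocol states no SD, so one must be assumed. The only value its figures imply comes from the non-inferiority calculation (margin 8, n = 35, one-sided 5%, 85% power):

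SD = 8 × sqrt(35/2) / (1.645 + 1.036) = 33.47 / 2.681 = 12.48

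Take the cited 8-point difference from sham as the effect. Power per comparison is Phi(8 / (SD × sqrt(2/n)) − critical value), with critical value 1.960 at 5% and 2.241 at 0.025. At SD 12.48 and n = 35 the SE is 2.984 and 8 / 2.984 = 2.681. This gives Phi(0.721) = 76% at 5% and Phi(0.440) = 67% at 0.025. A t-test gives 75.3% and 65.2%.

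| SD | n per arm | Power at 0.05 | Power at 0.025 |
|---|---|---|---|
| 8 | 35 | 99% | 97% |
| 10 | 35 | 92% | 87% |
| 12.5 | 35 | 76% | 67% |
| 12.5 | 42 | 84% | 76% |

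The last row takes all 126 randomized patients as observed (126 / 3 = 42): SE = 2.724, and 8 / 2.724 = 2.937.

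With 35 per arm, 95% power requires an SD of at most 33.47 / (1.960 + 1.645) = 9.3 at 5%, or 33.47 / (2.241 + 1.645) = 8.6 at 0.025.

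**4. Both trainings beating sham.** The two contrasts share the sham arm, so with equal arms their correlation is 0.5. If both trainings have an 8-point effect, SD is 12.5 and n is 35, the joint power is 64% at 5% and 52% at 0.025.

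**The case against.** Four points can fairly be made for the plan.

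- **Exergames versus sham is covered by implication.** The non-inferiority calculation assumes no true difference between exergames and adaptive COGNI-TRAcK. With equal arms and the same sham group, the power for adaptive versus sham then carries over to exergames. This stands. What is missing is the statement and an effect for that contrast, and the carried-over power is still for responders at 5%.
- **The SD of 12.5 is not the protocol's.** It is back-solved from rounded figures, and the protocol does not say whether it would apply to scores or to changes. The calculation also fixes n at 35, although all randomized patients are to be analysed and those who stop training are asked to keep attending visits. This stands too, so the power is given as a range.
- **A separate analysis plan may describe a responder test.** It may, but the mismatch between the stated hypothesis and the stated endpoint and analysis lies within this protocol.
- **The responder hypothesis is at least written down.** It is, but only in the sample size section, with no matching endpoint or analysis.

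Two stronger readings are tempting and are not supported. First, a reader might infer that the sample size bases contradict each other: under normality and equal SDs, an 8-point shift with 10/14 and 3/14 responders implies SD = 8 / (0.566 + 0.792) = 5.9, against 12.5. But those proportions come from 14 patients per group, with exact 95% intervals of 42–92% and 5–51%. Counts of 8/14 and 5/14, well inside those intervals, would imply 8 / (0.180 + 0.366) = 14.7. That is not a contradiction. Second, a reader might infer that the responder rule is too lax, since eligibility requires "defined as a corrected score less than 38" and 10% of that is always under 4 points. The wording, "according to a responder definition of SDMT change approximating 4 points or 10% in magnitude", can be read as two near-equivalent expressions, and no baseline distribution is given from which to size an effect.

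**Conclusion.** The mismatch is real and rests on the protocol's text alone. The figure of more than 95% is right for a two-sided 5% responder comparison of adaptive and sham, and it does not describe the planned primary superiority tests. Exergames versus sham has no power statement.

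The size of the gap depends on an SD that the protocol does not give. For an 8-point effect and 35 per arm, per-comparison power at 0.025 runs from about 97% (SD 8) through 87% (SD 10) to 67% (SD 12.5). At SD 12.5 it rises to 76% if 42 per arm are observed. At SD 12.5 with 35 per arm, the chance that both trainings beat sham is about 52%, if both have the 8-point effect.

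A reader might infer that the trial is underpowered for superiority. The document does not establish that: with an SD of 8.6 or less, 35 per arm reaches 95% per comparison even at 0.025. What can be said is that the protocol gives no basis for the power of its primary superiority claim.

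**What to change.** In Sample size estimation, replace the responder calculation with the power of two Week 8 SDMT contrasts: adaptive versus sham and exergames versus sham. Use one stated SD with its source, shared with the non-inferiority calculation; an assumed effect for each contrast; and alpha 0.025. If both contrasts must succeed for the objective to be met, give the joint power as well. Keep the responder comparison only as a named secondary analysis under the cited definition, or drop it.

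The cost is a rewritten paragraph and a small table, with enrolment unchanged. The downside is that the stated superiority power may fall below 95%. If the SD of 12.5 were kept, 95% power per comparison at 0.025 would need 2 × 12.48² × (2.241 + 1.645)² / 8² = 73.5, so 74 per arm. The more practical course is therefore to report the lower figure.
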